Use of any non-cigarette nicotine products ¹⁴						•	•	•	•	•	•	•	•	•	•	•	
Serum Cotinine	• ¹⁵					•		•		•		•		•	•		

¹Randomization *may* occur at the SV2 visit *IF* subject can commit to a quit date that allows start of treatment the following day. In such cases all Day 0 (Randomization) procedures must be completed at the SV2 clinic visit.

²Clinic will telephone each subject towards the end of Day 1 (first day of treatment) to make sure subject has taken medication according to dosing schedule, answer any questions, assess for adverse events and any concomitant medications.

³The final day of treatment should be on Day 84. In order to ensure subject completes all treatment prior to assessments, the W12 visit is to be scheduled on Day 86 ± 1 Day. If subject discontinues the study prior to Week 12, complete the planned 12-week assessments at the time of discontinuing, and record on the Early Discontinuation CRF.

⁴ The Screening assessment for suicidal ideation (questions 1-5) will be asked in the temporal context of “within the past 3 months” and the Suicidal Behavior questions will be asked within the temporal context of “within lifetime” in order to fully evaluate current ideation or risk of suicide. Assessments conducted at Week 6 and Week 12 will ask all questions in the temporal context of “since last assessment” for suicidal ideation/risk.

⁵Physical exam may be conducted at either the SV1 or the SV2.

⁶ Urine pregnancy test kits supplied to site by central laboratory. All other testing performed by a central laboratory. Test results must be negative at the SV1 and D0 visit for inclusion into the study, excluding females who are surgically sterile (hysterectomy or tubal ligation) or are >2 years post-menopausal.

⁷ Drugs of abuse to include at a minimum amphetamines, methamphetamines, barbiturates, benzodiazepines, cocaine, ecstasy, opiates, and phencyclidine.

⁸ To include height at screening for BMI calculation.

⁹ There are two distinct diaries to be used: The screening smoking diary will capture daily cigarette consumption for 7 consecutive days so that an average can be obtained to assess Inclusion Criteria #2. The on-study treatment diary is to assess treatment compliance and will capture each study drug dose date and time.

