12.2. Detailed Description of Study Visits

12.2.1. Screening Phase (SV1 – SV2)

Screening assessments used to evaluate inclusion and exclusion criteria (SV1) can occur during 1 or more clinical visits over a 28-day period prior to randomization.

Screening (Day -28 to Randomization Day 0)

Study procedures include:

1. Written informed consent obtained.
2. Demographic data.
3. Document medical and psychiatric history (including, but not limited to, any diagnosis of schizophrenia or bipolar psychiatric illness, and any occurrences of panic attacks or post-traumatic stress disorder).
4. Document suicidal ideation, risk, intent, or attempt as determined via administration and assessment of the Screening C-SSRS questionnaire ([Appendix 1](#)).
5. Depression is to be assessed via subject's completion of the HADS questionnaire, using total score derived from the depression-related questions **only** ([Appendix 6](#)).
6. Physical examination.
7. Document any existing adverse events.
8. Concomitant medications.
9. Review of smoking history, to include year started smoking, information about previous quit attempts (and methods/treatments used), average number of cigarettes smoked per day over the past 30 days, and type of cigarettes typically smoked (regular vs menthol).
10. Provide smoking diary instructions to capture number of cigarettes smoked for 7 consecutive days. This diary will be reviewed at Screening Visit 2 to verify that Inclusion #2 is met (averaging at least 10 cigarettes per day over a 7 day period).
11. Expired CO.
12. Vital signs, including weight and height for BMI calculation.
13. Urine pregnancy for all female subjects, excluding those who are surgically sterile (hysterectomy or tubal ligation) or are > 2 years post-menopausal.
14. Drugs of abuse screen.
15. Hematology and Chemistry testing.
16. Serum collected and frozen for cotinine testing. Actual baseline cotinine testing will be completed only for subjects that are randomized (batch tested). NOTE: An additional minimum 1.0 mL serum will be frozen and stored by the central laboratory for possible Nicotine Metabolite Ratio (NMR) testing at baseline only. These serum samples will be destroyed for all subjects that are screen-fails.

17. 12-lead ECG.
18. Review all inclusion and exclusion criteria and if satisfied, schedule Screening Visit #2.

Screening Visit prior to randomization (SV2)

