12.2.2. Randomization

Randomization (Day 0)

Randomization must be performed within 5-7 days prior to the agreed upon quit date. All other screening evaluations must be completed with 28 days prior to the Randomization Day. Study treatment must start on the day after randomization.

Study procedures include:

1. Update concomitant medication(s).
2. Document any existing adverse events.
3. Vital signs, including weight.
4. Urine pregnancy for all female subjects, excluding those who are surgically sterile (hysterectomy or tubal ligation) or are > 2 years post-menopausal.
5. Expired CO.

Upon completion of procedures 1-5 above, assess for final confirmation/verification of eligibility (NOTE: The expired CO value on Day 0 does not need to meet screening criteria [≥ 10 ppm] unless this is the only pre-treatment CO value available). If confirmation supports inclusion, complete the following:

1. Subject to complete the following questionnaires:
 - a. Fagerström Test for Nicotine Dependence ([Appendix 2](#)).
 - b. Smoking Self-Efficacy questionnaire (SEQ-12) ([Appendix 3](#)).
 - c. Brief Questionnaire of Smoking Urges (QSU-Brief) questionnaire ([Appendix 4](#)).
 - d. Minnesota Nicotine Withdrawal Scale (MNWS) questionnaire ([Appendix 5](#)).
2. Provide subject with behavioral support information that includes counseling ([Appendix 7](#)). NOTE: it should be stressed to subjects that they must maintain their dosing schedule throughout the Treatment Period.

3. Randomize according to a pre-determined, blinded, randomization schedule (see Section 7.5) and obtain the first study treatment carton (Carton #1) which will contain treatment packs for Weeks 1-6.
4. Provide study treatment Week 1 and Week 2 packs and review dosing requirements. Review the layout and dosing instructions printed on the study treatment packs. Although packs will be marked with the week designation and dates, there will be times during the Treatment Period where a subject has multiple packs on hand. Review this with the subject and make sure it is understood that each pack must be completed for the designated time period before moving on to the next. Instruct subject that any/all packs in their possession must be brought back to the clinic at each visit and should never be thrown away. Used packs will be collected and all cartons and packs must be maintained by the site for drug accountability by the assigned study monitor.

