APPENDIX 1. COLUMBIA - SUICIDE SEVERITY RATING SCALE (C-SSRS)

The Columbia Suicide Severity Rating Scale (C-SSRS) provides a standardized method to assess both suicidal ideation and behaviour to identify those at risk for suicide.²¹ The questionnaire must be administered by trained study staff* at Screening and again at the Week 6 (Day 42) and Week 12 (Day 86) study visits. Assessments at Screening will utilize the “Screening” version of the form with ideation to be assessed in the past 3 months and suicidal behaviour within lifetime (the later assessment timing helps to discern if later positive assessments are possibly treatment emergent). Any “Yes” to question 4 or 5 OR “Yes” to any suicidal behaviour question with clear suicidal intent or previous attempt will be considered exclusionary for this study. Assessments at Week 6 (Day 42) and Week 12 (Day 86) study visits will utilize the “Since Last Visit” version of the form with timeframe to be “since last assessment”. Any “Yes” to question 4 or 5 OR “Yes” to any suicidal behaviour question at the Week 6 (Day 42) or Week 12 (Day 86) study visits requires reporting as an AE as well as referral to a qualified Mental Health Professional for follow-up.

*Training by study staff is to be documented via certification in past 1 year on the C-SSRS. Training can be obtained on-line (www.cssrs.columbia.edu/training/training-research-setting).

COLUMBIA-SUICIDE SEVERITY RATING SCALE (C-SSRS)

Screening

Version 1/14/09

Posner, K.; Brent, D.; Lucas, C.; Gould, M.; Stanley, B.; Brown, G.; Fisher, P.; Zelazny, J.; Burke, A.; Oquendo, M.; Mann, J.

Disclaimer:

This scale is intended to be used by individuals who have received training in its administration. The questions contained in the Columbia-Suicide Severity Rating Scale are suggested probes. Ultimately, the determination of the presence of suicidal ideation or behavior depends on the judgment of the individual administering the scale.

Definitions of behavioral suicidal events in this scale are based on those used in The Columbia Suicide History Form, developed by [name] and [name], Conte Center for the Neuroscience of Mental Disorders (CCNMD), New York State Psychiatric Institute, [name]. (Oquendo M. A., Halberstam B. & Mann J. J., Risk factors for suicidal behavior: utility and limitations of research instruments. In M.B. First [Ed.] Standardized Evaluation in Clinical Practice, pp. 103 -130, 2003.)

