4.2.1.3. Other Adverse Events of Special Interest

The following events will be reported as “other adverse events of special interest”:

- Treatment-emergent suicidal ideation or risk, as measured by responses on the C-SSRS on or after first dose of study drug. Suicidal ideation or risk will be defined as a response of “Yes” to either question 4 or question 5 or “Yes” to any suicidal behavior question on the C-SSRS.

Note: Suicidal ideation or risk for suicide prior to randomization (“Yes” to either question 4 or question 5 OR “Yes” to any suicidal behavior question on the C-SSRS) is an exclusion criterion.

- Treatment-emergent moderate to severe depression, as measured by a HADS depression score ≥ 11 on or after first dose of study drug.

Note: Current symptoms of moderate to severe depression prior to randomization (HADS depression score ≥ 11) is an exclusion criterion.

- New pregnancy documented by a positive pregnancy test on or after first dose of study drug.

Note: Pregnancy is an exclusion criterion.

- Treatment-emergent coronavirus disease 2019 (COVID-19) will be selected using the Medical Dictionary for Regulatory Activities (MedDRA) standardized MedDRA query (SMQ) for COVID-19.

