The QSU-Brief is a 10-item questionnaire that will be administered Day 0, and at various visits during the treatment period (Day 2, Week 1 through Week 6). Item scores will be assigned using the scoring key pre-printed on the questionnaire (see Appendix 4 of the study protocol). A total QSU-Brief score will be derived for each subject, providing all questions have been answered.

Minnesota Withdrawal Scale (MNWS)

The MNWS is a 9-item questionnaire that will be administered at Day 0, and at various visits during the treatment period (Week 1 through Week 7). Item scores will be assigned using the scoring key pre-printed on the questionnaire (see Appendix 5 of the study protocol). A total MNWS score will be derived for each subject, providing all questions have been answered.

Columbia Suicide Severity Rating Scale (C-SSRS)

The C-SSRS (see Appendix 1 of the study protocol) is an assessment of both suicidal ideation and behavior. Suicidal ideation or risk for suicide (“Yes” to either question 4 or question 5 OR “Yes” to any suicidal behavior question on the C-SSRS) is an exclusion criterion.

The “Screening” version of the C-SSRS assesses suicidal ideation over the past 3 months, and suicidal behavior over the subject’s lifetime. The “Screening” version of the C-SSRS will be administered at SV1. The “Since Last Visit” version of the C-SSRS evaluates both suicidal ideation and behavior since the last assessment. This version of the C-SSRS will be administered at Week 6 and Week 12.

C-SSRS Suicidal Ideation: In both the “Screening” and “Since Last Visit” forms, there are 5 items that assess suicidal ideation. Subjects indicate (Yes/No) whether each of the following applies:

1. Wish to be dead
2. Non-specific active suicidal thoughts
3. Active suicidal ideation with any methods, without intent to act
4. Active suicidal ideation with some intent to act, without specific plan

5. Active suicidal ideation with specific plan and intent.

Each item will be assigned a numeric score (0=No, 1=Yes).

C-SSRS Suicidal Behavior: In both the “Screening” and “Since Last Visit” forms, there are 5 items that assess suicidal behavior. Subjects indicate (Yes/No) whether each of the following applies:

1. Actual attempt (non-fatal)
2. Interrupted attempt
3. Aborted attempt
4. Preparatory acts or behavior
5. Suicidal behavior

Each item will be assigned a numeric score (0=No, 1=Yes).

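### Suicidality arising between the SV1 C-SSRS and the first dose is counted as treatment-emergent in the special-interest summary, because SAP 4.2.1.3 has no onset condition

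*Protocol*

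**What the plan says.** **Schedule.** Protocol Appendix 1 has the C-SSRS administered "at Screening and again at the Week 6 (Day 42) and Week 12 (Day 86) study visits". SAP 6.4.2 places the first of these: the Screening "version of the C-SSRS will be administered at SV1". Protocol 12.2.1 says the SV1 assessments "can occur during 1 or more clinical visits over a 28-day period prior to randomization", and 12.2.2 adds that "Study treatment must start on the day after randomization".

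**Look-back.** Table 4, footnote 4 says "Assessments conducted at Week 6 and Week 12 will ask all questions in the temporal context of" the time since the last assessment. SAP 6.4.2 agrees that the later form "evaluates both suicidal ideation and behavior since the last assessment".

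**Counting rule.** SAP 4.2.1.3 lists as a special-interest event "Treatment-emergent suicidal ideation or risk, as measured by responses on the C-SSRS on or after first dose of study drug". A case is a Yes to question 4 or 5 or to any behavior question. SAP 11.1.2 reports the number and percentage of such subjects by arm. The general TEAE rule in SAP 4.2.1.1 works differently: it compares the start date and time of the event with those of the first dose.

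**Day 0.** The procedures listed first in Protocol 12.2.2 are concomitant medications, existing adverse events, vital signs, pregnancy test and expired CO. The text continues: "Upon completion of procedures 1-5 above, assess for final confirmation/verification of eligibility". The C-SSRS is not among the Day 0 procedures.

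**The concern.** The special-interest definition is set by when the answer is given, but the question asked at Week 6 reaches back to SV1. A subject who had qualifying ideation after SV1 and before the first tablet, and who answers truthfully at Week 6, is counted as a treatment-emergent case.

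The form cannot sort this out by itself. Its ideation items carry no onset date, and only the most lethal actual attempt is dated.

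Suicidality is a named safety outcome of this trial, and few cases are likely, so one misplaced case could be visible in the table. The special-interest summary and the TEAE tables could also give different answers for the same subject. Appendix 1 explains the lifetime look-back at screening as a help in telling whether later positives are treatment-emergent, so the plan itself wants the distinction that this schedule leaves open.

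**Working it through.** The plan gives no figure to reproduce. The check is day arithmetic on the protocol's own numbering.

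**Inputs**
- Randomization is Day 0 and first dose is Day 1 (Protocol 12 and 12.2.2).
- The earliest SV1 is Day -28 (Protocol 12.2.1).
- The latest usual SV1 is about Day -7. This is an assumption: the 7-day smoking diary is kept between SV1 and SV2 (Table 4, footnote 10), and randomization may take place at SV2 (footnote 1). SV1 procedures may be spread over several visits, so this is a typical minimum rather than a strict one.
- The Week 6 visit is Day 42 ± 1 and the Week 12 visit is Day 86 ± 1.

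**Formulas**, with s the day of SV1
- Pre-dose days: g = 1 - s
- Week 6 look-back: 42 - s, with pre-dose share g/(42 - s)
- Whole period covered by the two post-baseline forms: 86 - s, with pre-dose share g/(86 - s). The Week 12 form starts at Week 6, so its own interval is entirely after first dose.

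| SV1 | g | Look-back to Day 42 | Share | Period to Day 86 | Share |
|---|---|---|---|---|---|
| Day -28 | 29 | 70 | 41% | 114 | 25% |
| Day -14 | 15 | 56 | 27% | 100 | 15% |
| Day -7 | 8 | 49 | 16% | 93 | 9% |

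Moving the Week 6 visit by one day changes its share by less than one percentage point (40.8-42.0% for Day -28, 16.0-16.7% for Day -7). A subject who leaves the study early has the Week 12 assessments at that time (Protocol 8.3.2). If that is before Week 6, the look-back still reaches SV1 and the pre-dose share is larger.

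**Effect on a ratio.** The documents give no suicidality rate. For illustration, assume that the pre-dose rate equals the placebo on-treatment rate and that the true on-treatment rate ratio is 2.0. With pre-dose share f, the observed ratio is 2(1 - f) + f = 2 - f.
- Week 6 form: 2 - 0.163 = 1.84 to 2 - 0.414 = 1.59
- Whole period to Day 86: 2 - 0.086 = 1.91 to 2 - 0.254 = 1.75

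**Effect on a difference.** The gap before dosing is the same by design in every arm. The same expected number of events is therefore added to each arm and cancels on subtraction, which leaves the risk difference essentially unchanged but noisier.

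**The case against.** The strongest reply is that the plan already has an onset-dated route. Appendix 1 requires a qualifying Yes at Week 6 or 12 to be reported as an adverse event. Protocol 14.2 requires the date and time of onset, and SAP 4.2.1.1 then decides emergence from that date. This stands. The TEAE tables can be right, provided that the subject can place the onset within a recall period of up to about 70 days. It does not repair the separate special-interest count, which takes no account of that date.

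A reader might infer more than the documents support:
- *That all suicidality before first dose is miscounted.* Qualifying ideation in the 3 months before SV1 and lifetime behavior are asked about at SV1 and handled by exclusion 10. Only the interval from SV1 to first dose is exposed.
- *That nothing is rechecked before dosing.* Adverse events are documented at SV2 and Day 0, eligibility is confirmed at Day 0, and there is a telephone call on Day 1. What is missing is a repeat of the structured instrument.
- *That the comparison between arms is biased.* SAP 11 plans no safety tests, and SAP 11.1.2 reports counts and percentages. A ratio formed from them is diluted, but a difference is not materially biased.
- *That the HADS has the same fault.* Its items describe present states and have no look-back to the last assessment, so this mechanism does not apply.

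One could also argue that the later form, titled Since Last Visit, refers to the previous clinic visit. Footnote 4, Appendix 1 and SAP 6.4.2 all say assessment, and the previous C-SSRS assessment is SV1. The other reading would also leave most of the first six weeks unasked.

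**Conclusion.** The point holds as a defect in one safety definition. Followed as written, the plan puts qualifying ideation or behavior that arises between SV1 and first dose into the treatment-emergent special-interest count, and that count can contradict the TEAE tables.

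Pre-dose time is about 16-41% of the Week 6 recall period and about 9-25% of the whole period to Day 86. These ranges rest on SV1 falling between Day -28 and about Day -7. The shares describe time, not events. Turning them into a diluted ratio needs the equal-rate assumption, which the documents neither support nor contradict.

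The expected effect is a somewhat inflated count in every arm. It should not be read as a bias for or against cytisinicline. A secondary consequence is that exclusion 10, which concerns current ideation, can rest on a structured answer up to 28 days old at randomization. The point is worth correcting because the outcome is a named one and the correction is cheap.

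**What to change.** **Preferred.** In Protocol Table 4 and section 12.2.2, add the Since Last Visit C-SSRS at Day 0, before randomization. The Week 6 look-back then starts at Day 0, and the existing exclusion 10 is confirmed on a current answer. In SAP 4.2.1.3 and 6.4.2, name Day 0 as the C-SSRS baseline. This fits the general baseline rule in SAP 6.3, which takes the last observation before first dose.

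**If Day 0 can no longer be changed.** Amend SAP 4.2.1.3 so that a qualifying response is treatment-emergent only if onset was on or after first dose, using the adverse-event onset date already collected. This aligns it with SAP 4.2.1.1 and corrects the count, but does not add the Day 0 check.

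**Cost.** The preferred change adds one short form at a visit that already includes four questionnaires, with staff whose C-SSRS certification is already required. A few subjects may fail screening late. The fallback costs one sentence in the SAP. The HADS schedule needs no change on this ground.

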12.2. Detailed Description of Study Visits

12.2.1. Screening Phase (SV1 – SV2)

Screening assessments used to evaluate inclusion and exclusion criteria (SV1) can occur during 1 or more clinical visits over a 28-day period prior to randomization.

Screening (Day -28 to Randomization Day 0)

Study procedures include:

1. Written informed consent obtained.
2. Demographic data.
3. Document medical and psychiatric history (including, but not limited to, any diagnosis of schizophrenia or bipolar psychiatric illness, and any occurrences of panic attacks or post-traumatic stress disorder).
4. Document suicidal ideation, risk, intent, or attempt as determined via administration and assessment of the Screening C-SSRS questionnaire ([Appendix 1](#)).
5. Depression is to be assessed via subject's completion of the HADS questionnaire, using total score derived from the depression-related questions **only** ([Appendix 6](#)).
6. Physical examination.
7. Document any existing adverse events.
8. Concomitant medications.
9. Review of smoking history, to include year started smoking, information about previous quit attempts (and methods/treatments used), average number of cigarettes smoked per day over the past 30 days, and type of cigarettes typically smoked (regular vs menthol).
10. Provide smoking diary instructions to capture number of cigarettes smoked for 7 consecutive days. This diary will be reviewed at Screening Visit 2 to verify that Inclusion #2 is met (averaging at least 10 cigarettes per day over a 7 day period).
11. Expired CO.
12. Vital signs, including weight and height for BMI calculation.
13. Urine pregnancy for all female subjects, excluding those who are surgically sterile (hysterectomy or tubal ligation) or are > 2 years post-menopausal.
14. Drugs of abuse screen.
15. Hematology and Chemistry testing.
16. Serum collected and frozen for cotinine testing. Actual baseline cotinine testing will be completed only for subjects that are randomized (batch tested). NOTE: An additional minimum 1.0 mL serum will be frozen and stored by the central laboratory for possible Nicotine Metabolite Ratio (NMR) testing at baseline only. These serum samples will be destroyed for all subjects that are screen-fails.

17. 12-lead ECG.
18. Review all inclusion and exclusion criteria and if satisfied, schedule Screening Visit #2.

Screening Visit prior to randomization (SV2)

1. During the Screening Visit document any existing adverse events and concomitant medications. **Note:** Subjects must have adequately completed the 7-day daily smoking diary and have reported smoking an average of at least 10 cigarettes on 7 consecutive days to be eligible for inclusion into the study.
2. Each subject to provide their quit date, which must be 5-7 days after randomization (Treatment Day 5, 6 or 7) and the quit date must be documented. Setting a quit date and plan will be considered as the initial behavioral support session with the subject. The quit date will then determine the date for randomization. If a subject can commit to a quit date that allows for treatment to start the following day, the Screening Visit may be treated as Day 0 and the subject can be randomized. In such cases, all procedures outlined in (Section 12.2.2) must be completed.

